## 4.0 Study Population

Physicians in training at Cedars Sinai.

#### 4.1 Inclusion Criteria

- Individuals 18 years old or older are included.
- Training physicians in Internal Medicine residency and Gastroenterology fellowship at Cedars Sinai.
- Study is limited to Cedars-Sinai employees who are known to speak English.
- HRP-514.2 academic HR compliance addendum review is attached (Appendix A)

#### 4.2 Exclusion Criteria

- Pregnancy
- Active treatment of severe and uncontrolled anxiety or depression with a health care professional
- Unwilling and or unable to participate
- Non-English speakers.

## 4.3 Subject Identification, Recruitment, and Consent

Subjects will be initially identified in the following ways:

• The study population will be identified from the internal medicine residency and gastroenterology fellowship roster at Cedars Sinai. All subject's will be invited to participate in this study. Subjects will be recruited through an e-mail sent to the group roster and through didactic announcements.

### 4.3.1 Consent Description

Informed consent will take place via e-consent through REDCap. Participants will be invited via e-mail to participate in the study. The email will be sent to the group email for Internal medicine residents and the group email for Gastroenterology fellows for inclusion and limiting perceived coercion as no one person will be emailed directly. If trainees have questions or concerns, they will be directed to contact a team members who is not involved in trainee education or employment.

#### **Potential Risks**

Artificial Intelligence mental health support: The AI system developed here at Cedars trained system here trained the test system to behave with beneficence and act according to professional standards for a psychotherapist, there is potential that the artificially intelligent therapist response to the participant's communications in a manner perceived to be offensive, incorrect, or potentially traumatic. These adverse responses may cause the participant emotional or psychological harm.

Questionnaire risks: The questionnaires could make participants feel uncomfortable or embarrassed.

#### **Potential Benefits**

We expected little to no immediate benefit to be incurred by exposure of participants to one 20-minute session of AI powered mental health support. However, those who complete the 4 sessions over the course of the 4 weeks may experience mental health benefits. The long-term potential benefit of this investigation is evaluating the safety and feasibility of AI-powered mental health support tool over the course of 4 weeks. In doing so, the overall benefits and limitations of this approach will be better understood for future investigations and potential implementation. Furthermore, the information yielded from this investigation will inform further research and development of AI powered mental health support, which, if proven efficacious and safe, has the potential to greatly increase accessibility to high-quality mental health support to physicians in training with limited free time.

#### ASSESSMENT OF POTENTIAL RISKS AND BENEFITS

The risk of the artificially intelligent therapist generating adverse responses/advice during the session is rationalized by the nature of the investigation being a feasibility study of the implementation of an Al-powered mental health support tool. We anticipate that the built-in safeguards which minimize the ability of the model to generate derogatory, unprofessional, or dangerous responses will greatly minimize the chances of this occurring. In internal pilot testing within our lab, which has included over 100 mock conversations to date, we have not yet experienced any perceived adversarial, derogatory, unprofessional, or harmful response or advice. Nonetheless, an important purpose of this feasibility study is to confirm safety and appropriateness of the system. Furthermore, the risk of emotional or psychological adverse events as a result of the interaction with the AI model will also be minimized by providing participants with access to a hot line (Appendix E) to licensed mental health workers who are available at all times free at charge to trainees at Cedars Sinai. At the beginning of each session, participants will be provided instruction on how to access the licensed mental health works should an adverse event occur. If participants feel they need immediate assistance or report concerning suicidal thoughts or ideation, XAIA can send an immediate text and email to our social worker who is not involved in trainee education and employment. Our social worker can then contact the trainee for immediate intervention and provide immediate psychiatric resources available to trainees. In addition, a psychiatrist who is not involved in the proposed participants training, will be available for any urgent psychiatric attention.

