- 2. Our social worker will be the only study members with a list of the subject's email and code.
- 3. Our social worker will review the survey responses on redcap.
- 4. If a participant survey has as a score on the PHQ9 >15 and or GAD>10, our social worker will contact the participant for evaluation and provide additional resources as needed.

5. During the sessions, XAIA will be programed to send a text message to our social worker from participants who report actionable comments such as suicidal thoughts and concerns. Our social worker will be available to receive the messages from XAIA and contact the trainee for immediate intervention and connect the trainee to additional resources as needed. In addition, a psychiatrist physician will be available for any urgent psychiatric attention.

The AI powered sessions will be administered via a web browser such as a computer, laptop, tablets or cellphone. Participants can complete the session in the privacy of their home or in a private location at work such as a call-room. Participants will be asked to complete one 20-minute session per week during the 4-week study period for a total of four sessions.

The AI program used will be the XAIA software program. XAIA was developed at Cedars Sinai. Participants will be sent an email with the link to use the XAIA software. This includes a tutorial on how to use XAIA. Typical interactions with XAIA involve a process of XAIA initially probing for topics with general inquiries "So [name], how can I help?", then asking more indepth questions about a particular topic identified by the participant, and then offering support and/or coping methods about the identified problem or topic. Once XAIA is done speaking, the participant will answer the questions and press the "done speaking" button. XAIA then processes the messages and then replies. This process repeats until the participant informs XAIA that they wish to end the session and can click the "end session" button.

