Conversations are processed through a HIPAA-compliant server: audio is recorded, transcribed by speech-to-text AI, and responded to by LLM (GPT-4). The LLM output is sent through an "Appropriateness Classifier"—a stand-alone AI to detect potentially dangerous or unhelpful responses. If triggered, the LLM is again queried, and its response is again analyzed. Otherwise, the output is released to a text-to-speech AI, which finally, together with sentiment analysis meta-data controlling XAIAs expressions, plays to the user. The system's development involved iterative testing with therapists role-playing clinical scenarios, leading to continuous refinement of its psychotherapeutic communication. The program compiles and records data through audio responses. The responses from the user are recorded in-app, encrypted, and sent to a speech-to-text AI model, the resulting text transcript is sent to the LLM, which replies with text that is then converted to speech and played back to the user. Both text from the user and the LLM are stored on HIPAA-compliant servers. All audio data is not stored. Investigators have no access to the encrypted data.

The duration of the study session is 4 weeks and total duration of the study is three months.

The study will be conducted at one site only, Cedars-Sinai or participants may conduct the sessions at the privacy of their own home.

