#### **Questionnaires/surveys:**

This study involves the administration of questionnaires to evaluate scoring changes for depression and anxiety symptoms as a measurement for mental health wellness before and after the intervention. This information is routinely collected as part of clinical care with the PHQ-9 and GAD-7 questionnaires. The questionnaires will be administered at baseline and at the end of the 4-week study period. As part of the initial questionnaire, there will be a set of questions that aim to determine demographics as well as work-related and home-related factors that contribute to mental health will be administered prior to the AI powered sessions. At the completion of the 4-week session a questionnaire with a set of questions evaluating the use and acceptability of the AI mental health support will be administered. Finally, participants will be sent a questionnaire including the PHQ-9 and GAD-7 along with a set of questions evaluating their interest in participating in additional sessions at 3 months. The follow-up questionnaires will also provide information on active resources for mental health available to trainees at Cedas Sinai. In total, the questionnaires should take no longer than 20 minutes to complete at the beginning and end of the study period and no longer than 10 minutes at followup. The questionnaire will be administered electronically via REDCap. The study will not collect personal identifying information. The questionnaire will also contain a link with information on how to obtain immediate mental health assistance including a hot line as provided by GME to all trainees at Cedars Sinai. This includes access to a mental health professional who is on call for any psychiatric emergencies.

We will be conducting following questionnaires.

- Patient Health Questionnaire -9 (PHQ-9) Will be administered at the beginning and end of the study as part of Appendix B, C and D.
  - o This questionnaire is validated.
  - o The questionnaire is available in languages other than English.
- General Anxiety Disorder- 7 (GASD-7) will be administered at the beginning and end of the study as part of Appendix B, C and D.
  - o This questionnaire is validated.
  - o The questionnaire is available in languages other than English.
- Work and Home Environment will be administered only at the beginning of the study as part of Appendix B.
  - o This questionnaire is not validated.

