## 7.0 Data and Safety Monitoring

### 7.1 Data and Safety Monitoring Plan

The study will be monitored by the PI to ensure appropriate study conduct, including obtaining proper access to data, compliance with the HIPAA Privacy Rule, compliance with Cedars-Sinai policy, and adhering to the plans outlined in the protocol for all study procedures, abstracting and recording data, data security and maintenance, and data accuracy and integrity. Any adverse events, deviations, protocol exception requests, potential unanticipated problems involving risks to subjects or others, or other events will be submitted to the IRB in accordance with IRB reporting policy.

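### Confirming the AI tool's safety and appropriateness is a stated purpose, but no described step records an inappropriate AI response as study data

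*Protocol*

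**What the plan says.** **Purpose.** The Assessment of Potential Risks and Benefits states that "an important purpose of this feasibility study is to confirm safety and appropriateness of the system". Potential Benefits likewise presents the evaluation of safety as a long-term gain.

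**Named hazard.** Potential Risks says that the AI may answer "in a manner perceived to be offensive, incorrect, or potentially traumatic", and that this could cause emotional or psychological harm.

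**What a participant is told.** At the start of each session, "participants will be provided instruction on how to access the licensed mental health works should an adverse event occur". Section 5.3 describes the service behind this as "a hot line as provided by GME to all trainees at Cedars Sinai".

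**In-session alerts.** Section 5.2, step 5, has XAIA send the social worker a message from "participants who report actionable comments such as suicidal thoughts and concerns". The risk-benefit assessment adds a wider trigger: the participant feels in need of immediate help.

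**Output screening.** Section 5.2 describes an Appropriateness Classifier, "a stand-alone AI to detect potentially dangerous or unhelpful responses". When it fires, the model is queried again and the new answer is screened in turn.

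**Data.** Section 5.2 says that user and AI text are stored but that investigators cannot access the encrypted data. Section 6.1 gives the questionnaires as the source of all data collected. Section 5.3 describes the four-week form as asking about use and acceptability, and the three-month form as PHQ-9, GAD-7 and interest in more sessions.

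**Reporting.** Section 7.1 sends to the IRB "Any adverse events, deviations, protocol exception requests, potential unanticipated problems involving risks to subjects or others", among other events.

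**The concern.** The study claims that it will confirm a property of the AI's output, yet describes no measurement of that property. Section 7.1 deals with events once they are known; it does not say how the study comes to know of them.

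A participant could receive an incorrect or offensive reply, close the session, perhaps call the hotline, and complete the remaining forms without being asked about it. Nothing in the plan as described would then bring the event to the PI or the IRB. A final statement that no inappropriate responses were observed could reflect the absence of a question as easily as the behaviour of the tool. Section 3.0 foresees a larger study if the sessions prove efficacious and feasible, so an uninformative zero could be carried forward as reassurance.

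**Working it through.** The Protocol states no event rate or safety bound, so there is no figure to reproduce. The check is to follow an inappropriate AI reply that the participant has heard through each described channel.

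| Channel | Where | Reaches a study member? | Described as recording the AI reply? |
|---|---|---|---|
| Hotline | Risk-benefit assessment; 5.3 | No report back described | No |
| XAIA alert | Risk-benefit assessment; 5.2 step 5 | Yes, the social worker, if the participant voices distress or asks for help | No |
| Contact after high PHQ-9 or GAD-7 scores | 5.2 steps 3–4 | Yes, the social worker | No; the scores do not attribute distress to a reply |
| Classifier | 5.2 | No log, count or review described | No; it acts before release |
| Stored text | 5.2 | Investigators have no access | No |
| Form at four weeks (Appendix C) | 5.3 | Yes | Not in the description; the form is not shown |
| Form at three months (Appendix D) | 5.3 | Yes | Not in the description; the form is not shown |

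Three points follow.

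1. The two channels that reach the social worker depend on the participant's words or scores. An incorrect reply that causes irritation but no crisis triggers neither.
2. A draft caught by the classifier is not released. A bad reply that the participant hears is one that the classifier passed, so trigger counts would describe the safeguard and not this harm.
3. The session form comes once, after four weeks. A participant who stops after a distressing session may never complete it.

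**Why a zero is uninformative (illustration only).** Let p be the true rate of inappropriate replies per session and c the probability that one is recorded. With 20 participants (8.1) and four sessions each (5.2), there are 20 × 4 = 80 sessions. If sessions are treated as independent, the chance of recording none is (1 − p·c)^80. The values of p and c are assumptions; the Protocol gives neither.

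- p = 2%, c = 1: 0.98^80 = 20%.
- p = 2%, c = 0.5: 0.99^80 = 45%.
- Any p, c = 0: 100%.
- With full capture (c = 1), p = 1% gives 45% and p = 5% gives 2%.

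The same observed zero can be fairly informative or say nothing, depending on c, and the Protocol describes nothing that fixes c. The 80 sessions are themselves nominal, because the Protocol Summary says at least four sessions per participant.

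**The case against.** The strongest reply is that the study is not blind to harm. The social worker is a study member, supplies the XAIA link, receives the alerts, reviews the survey responses and contacts high scorers. Section 5.3 asks for sessions between 0700 and 2000 so that the social worker and a psychiatrist can be reached. Section 4.3.1 directs trainees' questions or concerns to a team member outside their education and employment. Because the hazard is defined by how a reply is perceived, alerts driven by the participant are relevant. Appendix C is the natural place for a question on AI replies and may already contain one. The primary objective is acceptability and feasibility, not an event rate.

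Most of this stands, and it limits the point. A reader might infer that participants are left with the hotline alone, or that a harmful reply has no way of reaching the study. The documents do not support that: there are partial routes, and the unseen appendix may add another. A reader might also infer that classifier events are deliberately left uncollected. The Protocol does not say so; it only describes no log and limits data to questionnaires.

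The reply does not remove the gap between purpose and data. Support for a distressed participant is not a record of what the AI said, and none of the partial routes is described as producing one.

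**Conclusion.** The point holds as a gap in ascertainment. Safety and appropriateness are a stated purpose, and no described step turns an inappropriate AI reply into study data. As written, a count of zero could not support the claim that appropriateness was confirmed.

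The size cannot be given as a rate. It is tempting to put an upper confidence limit on zero events in 80 sessions. That would assume complete capture, which is the very thing in question, as well as independence between repeat sessions of the same person.

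The conclusion rests on the described content of the questionnaires. If Appendix C asks about inappropriate replies, what remains is smaller: participants who stop early, and the missing step from the social worker to the PI. Support for participants and the primary objective are not called into question.

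**What to change.** 1. **Ask.** Unless Appendix C already does so, add an item to Appendices C and D on whether any AI reply was offensive, incorrect or distressing. In each session email, name the social worker as the study contact for reporting such a reply, alongside the hotline details. Participants who stop early can then also report.
2. **Pass on.** State in 7.1 that the social worker forwards de-identified reports to the PI for the IRB reporting already required there, and list these reports in 6.1 as a data source.
3. **Or narrow the claim.** If neither is done, limit the safety sentence in the risk-benefit assessment to what is collected.

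Aggregate counts of classifier triggers are optional. They would need no transcript access, but should be labelled as describing the safeguard.

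The cost is Protocol wording, one added item on each of two existing forms, a line in the emails and slightly more participant burden. The social worker takes on the relay of any reports; the Protocol gives no basis for estimating that time. Investigators still see no conversation text.

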## 5.0 Study Design and Procedures

### 5.1 Schedule of Events

#### Legend

• **R** = Research item/procedure done only for research purposes and their costs are covered by the study. You are not responsible for the costs of these procedures.

Procedures	Screening Visit	Visit #1	Visit #2	Visit #3	Visit #4	3-month follow-up
Informed Consent	R					
Questionnaires	R				R	R
VR sessions		R	R	R	R	

### 5.2 Study Design and Duration

This is a prospective pilot study with internal medicine residents and gastroenterology fellows to evaluate the role of AI mental health support tool as a wellness resource.

Participants will be invited via e-mail to participate in the study. ]The invitation e-mail will describe the study and ask that those who meet exclusion criteria do not participate in this pilot study. The e-mail will also include a file with information of the study for participants to review including how study members are blinded and the de-coding process required for participants to be contacted by our social worker should they score  $\geq$ 15 on PHQ-9 and or  $\geq$ 10 on GAD-7. Those who choose to participate will be asked email our team member who is not involved in trainee education who will send the participants a REDCap link to the consent, survey and a code to be used in the survey.

Participants will be asked to complete a set of questionnaires (Appendix B, C and D) to evaluate their mental health and factors that contribute to mental health as well as four AI powered mental health support sessions over a four-week period. This will conclude the active phase of their participations. Participants will then be sent a questionnaire at 3 months from study initiation to complete a questionnaire evaluating their mental health and if they would be interested in additional AI powered mental health support sessions.

The questionnaires will be administered before the AI sessions and at the end of the study period to evaluate for changes in mental health scores. The questionnaires will include the validated PHQ-9 for a standardized depression score and the GAD-7 for a standardized anxiety score to evaluate symptoms related to depression and anxiety. In addition, a set of questions will focus on demographics, work and home environment to evaluate factors that may contribute to mental health prior to the AI sessions and a set of questions related to the AI sessions at the end of the study period. The questionnaire will be administered via REDCap.

To maintain subject safety and confidentiality the following work-flow will be followed.

- 1. Participants who choose to participate in the study will be given a redcap link for the consent form, survey and a code via e-mail. In order to complete the consent and survey, participants will have to enter the code provided to them.
- 2. Our social worker will be the only study members with a list of the subject's email and code.
- 3. Our social worker will review the survey responses on redcap.
- 4. If a participant survey has as a score on the PHQ9 >15 and or GAD>10, our social worker will contact the participant for evaluation and provide additional resources as needed.

5. During the sessions, XAIA will be programed to send a text message to our social worker from participants who report actionable comments such as suicidal thoughts and concerns. Our social worker will be available to receive the messages from XAIA and contact the trainee for immediate intervention and connect the trainee to additional resources as needed. In addition, a psychiatrist physician will be available for any urgent psychiatric attention.

The AI powered sessions will be administered via a web browser such as a computer, laptop, tablets or cellphone. Participants can complete the session in the privacy of their home or in a private location at work such as a call-room. Participants will be asked to complete one 20-minute session per week during the 4-week study period for a total of four sessions.

The AI program used will be the XAIA software program. XAIA was developed at Cedars Sinai. Participants will be sent an email with the link to use the XAIA software. This includes a tutorial on how to use XAIA. Typical interactions with XAIA involve a process of XAIA initially probing for topics with general inquiries "So [name], how can I help?", then asking more indepth questions about a particular topic identified by the participant, and then offering support and/or coping methods about the identified problem or topic. Once XAIA is done speaking, the participant will answer the questions and press the "done speaking" button. XAIA then processes the messages and then replies. This process repeats until the participant informs XAIA that they wish to end the session and can click the "end session" button.

Conversations are processed through a HIPAA-compliant server: audio is recorded, transcribed by speech-to-text AI, and responded to by LLM (GPT-4). The LLM output is sent through an "Appropriateness Classifier"—a stand-alone AI to detect potentially dangerous or unhelpful responses. If triggered, the LLM is again queried, and its response is again analyzed. Otherwise, the output is released to a text-to-speech AI, which finally, together with sentiment analysis meta-data controlling XAIAs expressions, plays to the user. The system's development involved iterative testing with therapists role-playing clinical scenarios, leading to continuous refinement of its psychotherapeutic communication. The program compiles and records data through audio responses. The responses from the user are recorded in-app, encrypted, and sent to a speech-to-text AI model, the resulting text transcript is sent to the LLM, which replies with text that is then converted to speech and played back to the user. Both text from the user and the LLM are stored on HIPAA-compliant servers. All audio data is not stored. Investigators have no access to the encrypted data.

The duration of the study session is 4 weeks and total duration of the study is three months.

The study will be conducted at one site only, Cedars-Sinai or participants may conduct the sessions at the privacy of their own home.

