## 8.0 Sample Size and Statistical Considerations

## 8.1 Sample Size

This is a single-site study at Cedars-Sinai. The sample size of this pilot study is 20 subjects.

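### Section 5.2 sets the social worker's score-triggered contact at PHQ-9 ≥15 / GAD-7 ≥10 in one place and at >15 / >10 in work-flow step 4

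*Protocol*

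**What the plan says.** Both statements stand in Protocol Section 5.2 (Study Design and Duration).

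- **Information file.** The invitation e-mail carries a file that explains, among other things, "the de-coding process required for participants to be contacted by our social worker should they score" 15 or more on PHQ-9 and/or 10 or more on GAD-7. Both signs are printed as ≥.
- **Safety work-flow.** It opens with "To maintain subject safety and confidentiality the following work-flow will be followed". Step 3 is "Our social worker will review the survey responses on redcap". Step 4 is "If a participant survey has as a score on the PHQ9 >15 and or GAD>10, our social worker will contact the participant for evaluation". Both signs are printed as >.

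The two scales are collected three times. Section 5.3 (Questionnaires/surveys) says "The questionnaires will be administered at baseline and at the end of the 4-week study period", and then "Finally, participants will be sent a questionnaire including the PHQ-9 and GAD-7 along with a set of questions" at 3 months. Section 8.1 says "The sample size of this pilot study is 20 subjects".

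**The concern.** The person acting, the action, the two scales and the two numbers are the same in both statements; only the inequality differs. Both are current text, and no other section restates the cut-off or says which version takes precedence.

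Step 4 is the only safeguard in the protocol that a PHQ-9 or GAD-7 score sets off, and it is the instruction staff would work from. Read literally, it leaves out participants exactly at a cut-off that the other statement includes. Confidentiality is involved too: contact requires de-coding, and participants are told in advance when that will happen. What they are told and what staff do should agree.

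**Working it through.** **The two rules side by side.** PHQ-9 and GAD-7 scores are whole numbers.

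| | PHQ-9 trigger | GAD-7 trigger |
|---|---|---|
| Rule A (information file) | 15, 16, … | 10, 11, … |
| Rule B (work-flow step 4) | 16, 17, … | 11, 12, … |

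Either scale is enough under both rules. They therefore disagree only when PHQ-9 ≤15 and GAD-7 ≤10, with at least one score exactly at its cut-off:

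- PHQ-9 15, GAD-7 5: contact under A, none triggered under B.
- PHQ-9 8, GAD-7 10: contact under A, none triggered under B.
- PHQ-9 15, GAD-7 10: contact under A, none triggered under B.
- PHQ-9 15, GAD-7 12: contact under both.

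This much follows from the text alone.

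**How many surveys might fall there.** The protocol gives only the sample size (20) and the three time points. Everything else here is an assumption:

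- score ranges 0–27 (PHQ-9) and 0–21 (GAD-7);
- negative-binomial scores truncated to those ranges, with mean and SD specified before truncation;
- the same mean (2 to 8) and SD (3 to 5) on both scales;
- a Gaussian copula with correlation 0 to 0.8.

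The share of surveys on which the rules differ is

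d = P(PHQ-9 ≤15 and GAD-7 ≤10) − P(PHQ-9 ≤14 and GAD-7 ≤9).

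As a worked case, take mean 8, SD 3, correlation 0. The four marginal probabilities are P(PHQ-9 ≤15) = 0.9875, P(GAD-7 ≤10) = 0.8046, P(PHQ-9 ≤14) = 0.9762 and P(GAD-7 ≤9) = 0.7098. Then d = 0.9875 × 0.8046 − 0.9762 × 0.7098 = 0.102 (0.1017 before rounding).

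| Mean / SD | d, correlation 0 | d, correlation 0.8 |
|---|---|---|
| 2 / 3 | – | 0.0085 (grid minimum) |
| 4 / 4 | 0.0269 | 0.0226 |
| 6 / 4.5 | 0.0498 | 0.0419 |
| 8 / 5 | 0.0721 | 0.0614 |
| 8 / 4 | 0.0850 | 0.0748 |
| 8 / 3 | 0.1017 (grid maximum) | – |

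From the minimum and maximum:

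- Baseline surveys affected: 20 × 0.0085 = 0.17 to 20 × 0.1017 = 2.03.
- Chance of at least one among 20 independent participants, 1 − (1 − d)^20: 0.157 to 0.883.
- All surveys, at most 20 × 3 = 60 with no dropout and the same distribution each time: 60 × 0.0085 = 0.51 to 60 × 0.1017 = 6.10. This counts surveys, not people.

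If the two scales may have different means and SDs within the same ranges, d runs from 0.0083 to 0.1049, which is 0.17 to 2.10 of 20 and 0.50 to 6.30 of 60. The equal-mean assumption does not drive the range.

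Most of d comes from GAD-7. At mean 8, SD 3, P(GAD-7 = 10) is about 9.5% and P(PHQ-9 = 15) about 1.1%. At mean 4, SD 4 they are about 2.2% and 0.6%.

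**The case against.** The strongest reply is that this is an editorial slip of one point per scale with little practical consequence. Step 3 has the social worker look at the survey responses with no score condition, so a participant at exactly 15 or 10 is still seen by the person who decides on contact. Step 4 does not forbid contacting anyone else, so contacting at ≥15 / ≥10 complies with both statements. Other protections do not depend on scores: the hotline, the XAIA alert for suicidal comments (step 5), the available psychiatrist, and the link to immediate help in the questionnaire itself (Section 5.3). No automated REDCap alert is described.

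All of that stands, and it limits the weight of the point. It does not remove the conflict. The alert depends on what is said in a session, the hotline and the link depend on the participant using them, and step 3 names no score at which contact must follow.

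The text was also read from PDF by a program, and an underlined > in step 4 could have lost its underline. That the ≥ signs earlier in the section were read correctly is only weak evidence against this, because they may have been typed differently. Only the source file can settle it.

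Finally, the numerical range is about twelve-fold and every distributional input is assumed. That is fair: the figures indicate scale only, and the finding rests on the wording.

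**Conclusion.** The inconsistency holds. As printed, the protocol has two thresholds for one safety action, and the operative step carries the less protective one. It should be fixed, though it is not grave: no endpoint, analysis or sample size depends on it. Under the assumptions above, the rules would differ on roughly 1 in 100 to 1 in 10 surveys, mainly through GAD-7 scores of exactly 10. The true number cannot be derived from the protocol.

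Confidence is medium because of the possible lost underline. The information file is also not shown, so its own wording is unknown; only the protocol's description of it could be compared.

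**What to change.** Check the sign in the source file of step 4. If it is indeed >, change the step to PHQ-9 ≥15 and/or GAD-7 ≥10, which matches the earlier statement in Section 5.2 and is the safer of the two rules. Use the same signs in the participant information file and in any REDCap alert that may be built from step 4.

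This is a one-line correction; the earlier statement stays as it is. The extra work for the social worker, under the stated assumptions, is about 0.2 to 2 contacts at baseline and about 0.5 to 6 over at most 60 surveys.
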